2.3.1.3. Coronavirus Disease 2019

The SARS-COV-2 disease (coronavirus disease 2019 [COVID-19]) global pandemic is active in many countries at the time of this protocol amendment. Given this unique circumstance, specific consideration has been given to the risks and benefits of the study as they may be related to COVID-19, and the global and local changes that exist as a result of the pandemic. This assessment is described in Section 10.7.

2.3.2. Benefit Assessment

The potential benefit of ALXN1820 treatment for SCD is being measured by assessments of anemia and hemolysis. An increase in hemoglobin by ≥ 1 g/dL from baseline is considered clinically meaningful. In addition, a positive treatment effect would also be shown by a decrease in hemolysis, including improvements in the serum levels of markers of hemolysis (ie, lactate dehydrogenase [LDH], indirect bilirubin, and haptoglobin). Other exploratory endpoints (vaso-occlusive crisis [VOC], etc.) may be assessed.

2.3.3. Overall Benefit: Risk Conclusion

ALXN1820 has been and is being evaluated in an ongoing Phase 1 Study ALXN1820-HV-101. Study ALXN1820-SCD-201 is the second human exposure to ALXN1820.

Study ALXN1820-SCD-201 will be conducted in patients with SCD, and dosing will be initiated based on review of safety, tolerability, and PK/PD data from Study ALXN1820-HV-101. The doses administered in the current study are expected to produce exposure lower than the highest exposure tested in Study ALXN1820-HV-101, and the expected exposure in patients will be lower than the NOAEL exposure established in 6-week and 6-month GLP monkey toxicology studies. Strict inclusion/exclusion criteria, with a robust safety monitoring and risk mitigation plan are in place. A DMC will evaluate the available study data at prespecified time points for participant safety and make recommendations on dose modification or termination of the study. The selected doses are intended to deliver complete inhibition of properdin, providing potential benefit of ALXN1820 to patients with SCD, with a positive benefit/risk ratio.

The data obtained from this study is expected to inform future clinical studies in patients with SCD.

3. OBJECTIVES AND ENDPOINTS

The study objectives and corresponding endpoints are presented in Table 10.

Table 10: Mapping Objectives to Endpoints for Patients with Sickle Cell Disease

Objectives	Endpoints
Primary	
To assess the safety and tolerability of ALXN1820 SC in patients with SCD	Safety assessed by incidence of TEAEs and SAEs, physical examination, vital sign measurements, clinical laboratory, and electrocardiogram results through Day 211 (Cohorts 1 and 2) and through Day 169 (Optional Cohort 3)
Secondary	
To assess the multiple-dose PK of ALXN1820 SC	Serum ALXN1820 multiple-dose PK profiles through Day 211 (Cohorts 1 and 2) and through Day 169 (Optional Cohort 3)
To assess the PD effects of ALXN1820 SC	Change in serum concentrations of total and free properdin over time through Day 211 (Cohorts 1 and 2) and through Day 169 (Optional Cohort 3) Change in CAP activity using the Wieslab AP assay through Day 211 (Cohorts 1 and 2) and through Day 169 (Optional Cohort 3)
To assess the effect of ALXN1820 on complement biomarkers	Change from baseline in complement biomarkers through Week 12 (Cohorts 1 and 2)
To assess the effect of ALXN1820 on hemolysis	Change from baseline in hemoglobin levels at Week 12 (Cohorts 1 and 2) Change from baseline in hemolysis markers (eg, lactate dehydrogenase, reticulocytes, and bilirubin) and hemopexin at Week 12 (Cohorts 1 and 2)
To assess the immunogenicity of ALXN1820 SC	Incidence of ADAs to ALXN1820 through Day 211 (Cohorts 1 and 2) and through Day 169 for Optional Cohort 3
Exploratory	
To explore the effect of ALXN1820 on vaso-occlusion markers	Change from baseline in VOC related biomarkers through Week 12 (Cohorts 1 and 2)
To explore the clinical efficacy of ALXN1820 SC in SCD	VOC events (rate of VOC, time to first VOC) through Week 12 (Cohorts 1 and 2)

Abbreviations: ADA = antidrug antibody; AP = alternative pathway; CAP = complement alternative pathway; PD = pharmacodynamic(s); PK = pharmacokinetic(s); SAE = serious adverse event; SC = subcutaneous; SCD = sickle cell disease; TEAE = treatment-emergent adverse event; VOC = vaso-occlusive crisis.

4. STUDY DESIGN

4.1. Overall Design

This is a Phase 2a study, with up to 3 multiple dose cohorts of open-label ALXN1820 SC in adult patients with SCD (HbSS and HbS β^0 -thalassemia).

The study will be conducted in up to 30 adult patients with SCD enrolled in up to 3 open-label cohorts (Cohorts 1, 2 and 3 [optional]) to receive multiple SC doses of open-label ALXN1820. ALXN1820 will be administered as described in Table 11.

Table 11: ALXN1820-SCD-201 Dosing Cohorts

Cohort	N	Study Drug	Route of Administration	Planned Dose	Number of Doses/Dose Interval
1	Up to 12 maximum of 6 on stable dose of hydroxyurea	ALXN1820	SC	300 mg	QW \times 13
2	Up to 12 maximum of 6 on stable dose of hydroxyurea	ALXN1820	SC	600 mg	Q4W \times 4
3 (optional)	Up to 6 maximum of 3 on stable dose of hydroxyurea	ALXN1820	SC	300 mg	Q2W \times 4

Abbreviations: N = number of participants; QW = once weekly; Q2W = once every 2 weeks; Q4W = once every 4 weeks; SC = subcutaneous.

The dose and dosing intervals for Cohorts 1 and 2 were determined using cumulative safety data, an interim PK/PD analysis from participants enrolled in Study ALXN1820-HV-101, and data from the 6-month GLP toxicology study in monkeys. Optional Cohort 3 will be initiated after evaluation of safety and PK/PD data from Cohorts 1 and 2.

Cohort 1 and Cohort 2 will run in parallel, and patients will be randomized 1:1 to either of the cohorts on determination of eligibility. The decision to initiate Optional Cohort 3 will be made at Alexion's discretion and will be based on analysis of PK/PD and safety after at least 8 patients from Cohorts 1 and 2 (4 from each cohort) have enrolled. Furthermore, enrollment of Optional Cohort 3 will start after Cohorts 1 and 2 are fully enrolled. Each cohort will be stratified to ensure patients with SCD who are treated with a stable dose of hydroxyurea and patients with SCD who are not currently treated with hydroxyurea are included. For patients who were previously treated with hydroxyurea but are not currently on hydroxyurea, treatment must be stopped at least 30 days prior to providing informed consent.

This study will use an independent DMC to monitor safety and to perform the planned interim analyses of the study. At Alexion's discretion, and after consultation with the DMC, additional

participants with SCD may be enrolled as replacement participants if a participant discontinues during the Dosing Period for reasons other than drug related AEs.

4.2. Scientific Rationale for Study Design

The initial indication for ALXN1820 will be SCD. SCD affects about 20 to 25 million people worldwide (Aliyu, 2008) and in the US, approximately 100,000 people are affected (Hassell, 2010). The prevalence of SCD newborns and SCD carriers in the EU is approximately 1 to 5 in 10,000 and 1 in 150, respectively (Engert, 2016). The few available life expectancy estimates for SCD patients in the US or EU vary widely from 45 to 65 years which is approximately 20 years lower than the general population (Gardner, 2016; Lubeck, 2019; Payne, 2020; Platt, 1994).

SCD is a group of inherited disorders. A mutation in the β -hemoglobin gene is responsible for the synthesis of sickle hemoglobin (HbS). The most common genotypes in SCD are HbSS, HbSC, and HbS β^+ thalassemia. The most common clinical manifestations of SCD are chronic hemolysis and VOC (Kato, 2018; Pecker, 2021).

HbS has abnormal physicochemical properties and is prone to polymerization under low oxygen concentration causing deformation of red blood cells (RBCs) with the characteristic sickle shape. Sickling has numerous adverse outcomes on RBCs and on multiple organs. Sickled RBCs have limited life span due to hemolysis. Hemolysis is thought to occur principally through extravascular phagocytosis (approximately 2/3) and intravascular (approximately 1/3) hemolysis, which leads to anemia. Intravascular hemolysis of sickle RBCs leads to release of free hemoglobin, which in turn activates CAP (via free heme) and depletes nitric oxide, contributing to endothelial damage. Hemolysis and sickling of the RBCs leads to endothelial cell activation with increased adhesion molecule expression and activation of neutrophils, monocytes, and platelets (Kato, 2018). VOC, as a result of these processes, leads to obstruction of blood flow to vital organs such as the kidneys, liver, lungs, and heart, promoting ischemia, acute episodes of pain, and necrosis. The ensuing ischemic/reperfusion injury leads to the generation of reactive oxygen species. This in turn leads to a chronic inflammatory state (Kato, 2018; Piel, 2017). Patients also have increased vulnerability to infections, particularly from encapsulated bacteria, as a result of functional or actual asplenia. Together, these mechanisms contribute to the development of chronic organ damage including sickle nephropathy, pulmonary hypertension, avascular necrosis of the bone, chronic lung disease, and shortened life expectancy (Kato, 2018).

Universal newborn screening is established in the US to enable early diagnosis and treatment of infants with SCD to reduce morbidity and mortality. It is recommended that all infants with HbSS and HbS β^0 -thalassemia receive penicillin prophylaxis and 23-valent-pneumococcal polysaccharide vaccine to prevent invasive pneumococcal disease (Kato, 2018; Pecker, 2021).

Hydroxyurea, RBC transfusion, and opioids are the treatments commonly used to manage the symptoms of SCD. There are several approved novel drugs for the treatment of sickle cell complications in recent years: L-glutamine (Endari[®]), voxelotor (Oxbryta[®]), and crizanlizumab (Adakveo[®]). However, none of these treatments addresses both anemia (hemolysis) and VOC. The only curative treatment option for SCD is hematopoietic stem cell transplantation. However, this is reserved for severe patients due to the risk of life-threatening complications (Pecker, 2021).

Recently, much attention has been given to the role of the innate immune system in SCD, and in particular the role of complement activation in the pathophysiology of SCD (Tampaki, 2021; Varelas, 2021). In Investigator-initiated studies, eculizumab has demonstrated clinical effect in SCD patients with delayed hemolytic transfusion reaction, VOC, and drug-induced immune hemolytic anemia (Chonat, 2020). Compared to C5 inhibitors, CAP inhibitors have potential advantages in treatment of SCD. An increasing number of publications supports the hypothesis that sickle RBCs are the focal point of CAP activation, which triggers C3 opsonization on the cell surface as well as complement-mediated RBC hemolysis. Intravascular hemolysis is one of the main causes of anemia and also contributes to further amplification of CAP activation by releasing free heme from RBCs. C3 opsonization of sickle RBCs also promotes anemia through extravascular hemolysis via the reticuloendothelial system. Furthermore, C3 opsonization has been shown to be a key contributor to VOC. It has also been demonstrated that C3 opsonization can be precipitated by exposure of phosphatidyl serine on sickle RBCs and contributes to VOC by enhancing its interaction with adhesion molecules such as P-selectin and complement receptor 3 on activated endothelial cells (Lombardi, 2019). Thus, SCD nonclinical literature collectively underscores the role of CAP activation in SCD pathophysiology.

ALXN1820 binds with high affinity to human properdin, which is a component of the CAP, preventing it from stabilizing the CAP C3 and C5 convertases that cleave C3 and C5 into their activation products. By binding properdin, ALXN1820 prevents activation of the alternative complement system and thereby has the potential to treat SCD. In support of this, studies carried out at Alexion in a mouse model of SCD demonstrated that pretreatment of animals with an mouse anti-properdin antibody significantly ameliorated signs of hemolysis and vaso-occlusion, which are 2 main clinical features of SCD.

The current nonclinical data and data from the first in human study ALXN1820-HV-101 support further investigation of ALXN1820 as a potential for treatment of patients with SCD. This study is designed to allow preliminary evaluation of changes in SCD disease-related biomarkers and will guide the design of further clinical studies in patients with SCD.

4.3. Justification for Dose

The dose and the frequency of dosing will be based on all available data including the overall safety, tolerability, PK/PD modeling from the ongoing cohorts in Study ALXN1820-HV-101; available nonclinical data including PK, PD, and efficacy in SCD mouse models, and toxicology data from the GLP 6-week and 6-month studies in cynomolgus monkeys.

A preliminary PK/PD model has been established based on data from Study ALXN1820-HV-101 in healthy participants. This semi-mechanistic model assumed monovalent ALXN1820 binding to trimeric properdin with 3 binding sites. The relationship between free properdin and CAP activity was characterized by a sigmoidal E_{max} model. The model provided good fits to the observed data (ALXN1820, total and free properdin, and CAP activity) judged by the model diagnostics. To estimate the therapeutic dose in SCD patients, the following assumptions have been made:

- Complete suppression of CAP activity (<1% of baseline activity) is needed for clinical efficacy based on data from mouse SCD model (described in detail in the ALXN1820 IB)

- The baseline properdin concentration is about 20% higher in sickle cell patients than in healthy subjects (Strauss, 1977)

In addition, ALXN1820 clearance in sickle cell patients was set as similar to or 40% higher (seen in other antibody treatments for SCD (Crizanlizumab, 2019)) than that of the healthy participants to evaluate the impact of increased clearance on exposure and CAP inhibition. Based on these assumptions and analysis, it is predicted that a dose of 300 mg QW could inhibit the CAP activity to < 1% of the baseline values (upper limit of the 90% prediction interval) and maintain this effect during the Treatment Period. A dose of 600 mg Q4W or 300 mg Q2W was also shown to inhibit the CAP activity < 1% during majority of the dosing interval. The CAP activity will slowly recover and return to baseline after terminating dosing of ALXN1820. The safety margin at 300 mg QW is approximately 30-fold based on the NOAEL exposure established in the 6-month (or 26-week) monkey toxicology study. The safety margin at 600 mg Q4W or 300 mg Q2W is approximately 60-fold, based on the NOAEL exposure.

4.4. End of Study Definition

A participant is considered to have completed the study if he/she has completed all phases of the study including the last scheduled procedure shown in the SoA (Section 1.3).

The end of the study (EOS) is defined as the date the last participant completes the last visit as shown in the SoA (Section 1.3).

5. STUDY POPULATION

Prospective approval of protocol deviations to recruitment and enrollment criteria, also known as protocol waivers or exemptions, is not permitted.

5.1. Inclusion Criteria

Age

1. Participant must be 18 to 65 years of age inclusive, at the time of signing the informed consent.

Type of Participant and Disease Characteristics

2. Confirmed diagnosis of SCD (HbSS, or HbS β^0 -thalassemia).

Weight

3. Body weight \geq 40 kg (inclusive) at Screening.

Sex

4. Contraceptive use by men or women should be consistent with local regulations regarding the methods of contraception for those participating in clinical studies. Female participants of childbearing potential and male participants with female partners of childbearing potential must be willing to follow protocol-specified contraception guidance while on treatment and for at least 6 months after last dose of study drug (described in Section 10.4).

Other Inclusion Criteria

5. Hemoglobin between 5.5 and 10 g/dL at Screening.
6. Have had 1 to 10 VOCs in the past 12 months.
7. Patients receiving hydroxyurea must have been on a stable dose for \geq 3 months prior to providing informed consent, with no anticipated need for dose adjustment during the study. For patients who previously used hydroxyurea but are not currently on hydroxyurea treatment (due to non-responsiveness, intolerance, or unwillingness to take hydroxyurea), hydroxyurea treatment must have been discontinued at least 30 days prior to providing informed consent.
8. Patients will be vaccinated with MCV4 and serogroup B meningococcal vaccinations at least 14 days before dosing, if not already vaccinated within 3 years before the first dose (or per national/local guidelines). Participants who initiate study intervention treatment less than 14 days after receiving a meningococcal vaccine must receive treatment with appropriate prophylactic antibiotics until at least 2 weeks after vaccination.
9. *Haemophilus influenzae* type b (Hib) and *Streptococcus pneumoniae* vaccination are up to date according to current national/local vaccination guidelines for patients with SCD.
10. Must be willing to abide by all study requirements and restrictions.

Informed Consent

11. Capable of giving signed informed consent (or assent, as applicable) as described in Section 10.1.3, which includes compliance with the requirements and restrictions listed in the ICF and in this protocol.

5.2. Exclusion Criteria

Participants are excluded from the study if any of the following criteria apply:

1. Planned initiation, termination, or dose alteration of hydroxyurea during the study.
2. Receiving Voxelotor (OXBRYTA) or crizanlizumab (ADAKVEO) within 60 days of providing informed consent.
3. Receiving treatment with recombinant human erythropoetins (eg, epoetin alfa).
4. Treated with complement inhibitors within 6 months prior to the first dose.
5. Patients who are on chronic transfusion or receive a transfusion within 60 days of first dose.
6. Any significant disease or disorder which, in the opinion of the Investigator, may put the participant at risk.
7. History of complement deficiency.
8. History of *N meningitidis*, *S pneumoniae*, or *H influenzae* infection.
9. History of malignancy with the exception of a nonmelanoma skin cancer or carcinoma *in situ* of the cervix that has been treated with no evidence of recurrence within 5 years.
10. Evidence of hepatitis B (positive hepatitis surface antigen [HBsAg] or positive core antibody (anti-HBc) with negative surface antibody [anti-HBs]) or hepatitis C viral infection (hepatitis C virus [HCV] antibody positive, except for patients with documented successful treatment and documented sustained virologic response) at Screening.
11. Active systemic bacterial, viral, or fungal infection within 14 days prior to dosing.

Prior/Concurrent Clinical Study Experience

12. Participation (ie, last protocol-required study visit) in a clinical study within 90 days or 5 half-lives of the investigational agent, whichever is longer, before initiation of dosing on Day 1.
13. Participation in more than 1 clinical study of a monoclonal antibody (mAb), or participation (ie, last protocol required study visit) in a clinical study of a mAb within the 6 months or 5 half-lives of the mAb, whichever is longer, prior to Screening, during which the participant was exposed to the active study drug.

Diagnostic assessments

14. Severe renal impairment (estimated glomerular filtration rate [eGFR] < 30 mL/min/1.73 m²) or on chronic dialysis.

Other Exclusions

15. Female participants who are pregnant or breastfeeding.
16. History of allergy or hypersensitivity to excipients of ALXN1820 (eg, polysorbate 80).

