Cohort 1 and Cohort 2 will run in parallel, and patients will be randomized 1:1 to either of the cohorts on determination of eligibility. The decision to initiate Optional Cohort 3 will be made at Alexion's discretion and will be based on analysis of PK/PD and safety after at least 8 patients from Cohorts 1 and 2 (4 from each cohort) have enrolled. Furthermore, enrollment of Optional Cohort 3 will start after Cohorts 1 and 2 are fully enrolled. Each cohort will be stratified to ensure patients with SCD who are treated with a stable dose of hydroxyurea and patients with SCD who are not currently treated with hydroxyurea are included. The Treatment Period will be 12 weeks for Cohorts 1 and 2, and 6 weeks for Cohort 3. For patients who were previously treated with hydroxyurea but are not currently on hydroxyurea, treatment must have been stopped at least 30 days prior to providing informed consent.

At Alexion's discretion, and after consultation with the Data Monitoring Committee (DMC), additional participants with SCD may be enrolled as replacement participants if a participant discontinues during the Dosing Period for reasons other than drug-related adverse events (AEs).

Disclosure Statement This is an open-label, parallel group intervention study with up to 3 treatment arms.

Number of Participants:

Up to 30 adult patients with SCD (HbSS and HbSβ⁰-thalassemia) will be enrolled in up to 3 cohorts and will receive multiple open-label SC doses of ALXN1820. The cohorts will enroll both patients with SCD who are being treated with a stable dose of hydroxyurea and patients with SCD who are not currently treated with hydroxyurea. For patients who were previously treated with but are not currently on hydroxyurea, treatment must have been stopped at least 30 days prior to providing informed consent.

Intervention Groups and Duration:

The planned study duration is approximately 38 weeks for Cohorts 1 and 2: up to 56 days (8 weeks) for Screening, 84 days (12 weeks) for the Treatment Period, and 126 days (18 weeks) for the Follow-up Period. Patients will attend outpatient visits during the Treatment and Follow-

up Period with the option to stay at the inpatient facility. The end of study (EOS) for each individual patient is anticipated to be Day 211 (210 days) or the timepoint at which complement activity has returned to a normal range or 80% of baseline if later than Day 211.

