1.3. Schedule of Activities (SoA)

The SoA for once weekly (QW) dosing for multiple-dose Cohort 1 for Screening through Day 85 is presented in [Table 3](#).

The SoA for once every 4 weeks (Q4W) dosing for multiple-dose Cohort 2 for Screening through Day 85 is presented in [Table 4](#).

[Table 5](#) presents the SoA for intensive PK/PD sampling for a subset of participants in Cohorts 1 and 2. [Table 6](#) presents the SoA for Cohorts 1 and 2 for Day 99 through the end of the Follow-up Period.

The SoA for once every 2 weeks (Q2W) dosing for optional multiple-dose Cohort 3 for Screening through Day 43 is presented in [Table 7](#). [Table 8](#) presents the SoA for Cohort 3 for Day 57 through the end of the Follow-up Period.

Table 3: Schedule of Activities – Screening Through Day 85 (Cohort 1) – QW Dosing

Study Day	Screening Day –56 to Day –1	Day 1	Day 8	Day 15	Day 22	Day 29	Day 36	Day 43	Day 50	Day 57	Day 64	Day 71	Day 78	Day 85
Window (Day)	NA	NA	± 1	± 1	± 1	± 1	± 1	± 1	± 1	± 1	± 1	± 1	± 1	± 1
Informed consent ^a	X													
Eligibility criteria ^b	X	X												
Randomization ^c		X												
Confirmation of or administration of meningococcal vaccination ^d	X													
Confirmation of or administration of HiB and S pneumoniae vaccination	X													
Medical history and demographics	X													
Physical examination	X	X												
Abbreviated physical examination						X				X				X
Height, weight, and BMI ^e	X	X				X				X				X
Hematology ^f	X	X				X				X				X
Clinical chemistry ^f	X	X				X				X				X
Coagulation ^f	X	X				X				X				X
Hepatitis B and C screen	X													
HIV (types 1 and 2) screen	X													
Serum/urine pregnancy test ^g	X	X				X				X				X

Table 3: Schedule of Activities – Screening Through Day 85 (Cohort 1) – QW Dosing

Study Day	Screening Day –56 to Day –1	Day 1	Day 8	Day 15	Day 22	Day 29	Day 36	Day 43	Day 50	Day 57	Day 64	Day 71	Day 78	Day 85
Window (Day)	NA	NA	± 1	± 1	± 1	± 1	± 1	± 1	± 1	± 1	± 1	± 1	± 1	± 1
Urinalysis (including spot urine)	X	X				X				X				X
Vital sign measurements ^b	X	X	X	X	X	X	X	X	X	X	X	X	X	X
Triplicate ECG ⁱ	X	X		X		X				X				X
Study drug administration QW		X	X	X	X	X	X	X	X	X	X	X	X	X
PK samples ^j		X		X		X		X		X		X		X
Blood sample for PD panel ^{j,k}		X		X		X		X		X		X		X
Injection site reaction ^l		X	X	X	X	X	X	X	X	X	X	X	X	X
Biomarkers ^m	X	X		X		X		X		X		X		X
Immunogenicity (ALXN1820 ADA) ⁿ		X		X		X								X
Assessment of VOC ^o	X	←Monitor continuously→												

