10.2. Clinical Laboratory Tests

- The protocol-required clinical laboratory tests detailed in Table 13 will be performed by a central laboratory unless otherwise specified.
- Protocol-specific requirements for inclusion or exclusion of participants are detailed in Section 5 of the protocol.
- Additional tests may be performed at any time during the study as determined necessary by the Investigator or required by local regulations.
- Pregnancy testing: Women of childbearing potential should only be enrolled after a negative serum pregnancy test result at Screening. Additional local urine pregnancy testing will be standard for the protocol unless serum testing is required by site policies, local regulation, or IRB/IEC and should be performed per the time points specified in the SoA (Section 1.3).

Table 13: Protocol-required Laboratory Assessments

Laboratory Assessments	Parameters
Hematology	Platelet count Red blood cell (RBC) count Hemoglobin Free Hemoglobin Hemoglobinopathy test (eg, hemoglobin electrophoresis, screening only) Hematocrit Haptoglobin Hemopexin RBC indices (MCV, MCH, % reticulocytes) White blood cell (WBC) count with differential (neutrophils, lymphocytes, monocytes, eosinophils, basophils)
Clinical chemistry	Alanine aminotransferase (ALT)/serum glutamic-pyruvic transaminase (SGPT) Alkaline phosphatase Aspartate aminotransferase (AST)/serum glutamic-oxaloacetic transaminase (SGOT) Blood urea nitrogen (optional) Calcium Creatinine Creatine kinase Hemoglobin A1C Fructosamine LDH Potassium Sodium Serum albumin

Table 13: Protocol-required Laboratory Assessments

Laboratory Assessments	Parameters
	Total and direct bilirubin Indirect bilirubin Total protein Urea
Coagulation	Prothrombin time, partial thromboplastin time, international normalized ratio
Routine urinalysis	Specific gravity pH, glucose, protein, blood, ketones, bilirubin, urobilinogen, nitrite, leukocyte esterase by dipstick Microscopic examination (If blood or protein is abnormal)
Spot urine studies	Protein, albumin, creatinine, and protein-to-creatinine and albumin/creatinine ratio
Complement activity	Change in CAP activity using the Wieslab AP assay
Biomarkers	Complement biomarkers Biomarkers related to VOC Other biomarkers may be considered if feasible

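### The 60-day transfusion-free window runs back from first dose, not from the Screening sample, so the qualifying hemoglobin can be drawn about 5 days after a transfusion

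*Protocol*

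**What the plan says.** - **Transfusion.** Protocol Section 5.2, criterion 5, excludes "Patients who are on chronic transfusion or receive a transfusion within 60 days of first dose". The reference date is first dose.
- **Hemoglobin limits.** Protocol Section 5.1, criterion 5, requires "Hemoglobin between 5.5 and 10 g/dL at Screening". The reference date is Screening.
- **Length of Screening.** The Synopsis allows "up to 56 days (8 weeks) for Screening", and the Schedule of Activities heads the column "Screening Day –56 to Day –1".
- **Transfusion during the study.** Section 6.5.2 bars transfusion in Screening and the Treatment Period and says that a patient who has one will be discontinued. Section 7.2.1 lists use of disallowed medication as a reason to consider discontinuation. Neither reaches back before Screening.
- **Re-checks.** The Schedule of Activities footnotes have eligibility assessed at Screening and again on Day 1. Section 5.4 lets the investigator repeat out-of-range Screening laboratory values.
- **Other windows.** Criterion 2 of Section 5.2 counts from consent: "Receiving Voxelotor (OXBRYTA) or crizanlizumab (ADAKVEO) within 60 days of providing informed consent". The hydroxyurea windows in Section 5.1, criterion 7, also count from consent.

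**The concern.** The hemoglobin floor of 5.5 g/dL is a statement about the patient's own disease. It works only if the sample reflects the patient's own red cells. Transfusion is the prior treatment that changes that reading most directly, yet its exclusion window protects the day of first dose and not the day on which the floor is applied.

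At stake is eligibility. A patient whose own hemoglobin is below the floor could qualify on a sample raised by a recent transfusion. As the donor cells are lost, that patient would be in a treatment period in which a further transfusion is not allowed and ends study treatment. The rule would then fail for the patients it is meant to keep out.

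**Working it through.** **Inputs from the documents.** Transfusion-free window: 60 days before first dose (Section 5.2). Screening: Day -56 to Day -1 (Section 1.3). Floor: 5.5 g/dL at Screening (Section 5.1).

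**Check of the plan's day count.** Day -56 to Day -1 is 56 days, or 56 / 7 = 8 weeks, as stated. Screening, treatment and follow-up sum to 56 + 84 + 126 = 266 days = 38 weeks, as stated. The end of study is "anticipated to be Day 211 (210 days"), and 84 + 126 = 210, so Day n lies n - 1 days after Day 1. With no Day 0, Day -k lies k days before Day 1.

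**Smallest gap.** If day 60 itself is barred, the latest permitted transfusion is 61 days before first dose. The earliest Screening sample is 56 days before.

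Gap = 61 - 56 = **5 days**.

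If a transfusion on day 60 is permitted, or if a Day 0 is counted, the gap is 4 days; if both, 3 days.

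**Effect on the floor.** The documents give no figure for the rise after a transfusion or for donor-cell survival. Assumptions: a rise of 1 g/dL, linear loss of donor cells over L = 60 to 120 days, and a constant native level.

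Fraction of the rise remaining = 1 - gap / L (zero once gap reaches L)

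Lowest native level that reads 5.5 g/dL = 5.5 - 1 × fraction

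| Screening sample | Gap (days) | Fraction, L = 60 | Fraction, L = 120 | Lowest native level (g/dL), L = 60 / L = 120 |
|---|---|---|---|---|
| Day -56 | 5 | 0.92 | 0.96 | 4.58 / 4.54 |
| Day -42 | 19 | 0.68 | 0.84 | 4.82 / 4.66 |
| Day -28 | 33 | 0.45 | 0.73 | 5.05 / 4.78 |
| Day -14 | 47 | 0.22 | 0.61 | 5.28 / 4.89 |
| Day -1 | 60 | 0.00 | 0.50 | 5.50 / 5.00 |

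The undercut is proportional to the assumed rise: half the rise gives 0.46 to 0.48 g/dL in the first row.

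**Does another clause close the gap?**

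- The Section 6.5.2 ban starts with Screening; the transfusion in question comes before it.
- The Day 1 eligibility check applies the criteria as written, and the hemoglobin criterion is written for Screening. A lower Day 1 value does not fail it.
- The repeat in Section 5.4 is optional, and a value that has just qualified gives no reason to ask for one.
- Section 8 lets a routine blood count taken before consent serve for Screening if it falls in the scheduled time frame. A count taken in ordinary care soon after a transfusion could therefore be the qualifying value.
- Section 5 rules out waivers, so the literal wording governs.

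None of these requires a transfusion-free interval before the qualifying sample.

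**The case against.** The strongest reply is that 5 days is a corner case. It needs an isolated transfusion on the last permitted day and a sample on the first Screening day. Patients on chronic transfusion are already excluded, the investigator can exclude anyone judged at risk (Section 5.2, criterion 6), and eligibility is looked at again on Day 1. The anchor is not odd in itself either: criteria 4, 11 and 12 of Section 5.2 also count from first dose or dosing, so the contrast with criterion 2 proves little.

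Much of this stands. The gap is usually longer than 5 days, few candidates would be affected, and an attentive investigator could catch them. But each safeguard depends on discretion or does not reach the hemoglobin criterion as worded. The other first-dose windows do not concern a treatment that directly changes the measured hemoglobin.

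A reader might also infer three stronger things that the documents do not support:

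- **That the Week 12 hemoglobin change, or its power, is compromised.** SAP Section 4.1 takes baseline as the last available value before first dose, and hematology is scheduled on Day 1. Baseline is therefore normally at least 61 days after any transfusion, whenever the Screening sample was drawn. Any donor cells left on Day 1 reflect the length of the first-dose window, which is a separate matter.
- **That the qualifying sample is mostly donor blood.** On the assumptions above, the donor share is 0.92 / 5.5 to 0.96 / 5.5, about 17%.
- **That the genotype criterion is undermined.** Table 13 lists "Hemoglobinopathy test (eg, hemoglobin electrophoresis, screening only"), but Section 5.1 asks only for "Confirmed diagnosis of SCD (HbSS, or HbS"β0-thalassemia) and does not say that the Screening test must supply the confirmation. An existing record could serve. Both genotypes are eligible, so confusing one with the other admits nobody wrongly.

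**Conclusion.** The point holds as a narrow eligibility gap. The 5-day minimum follows from the protocol's own day counts, with 3 to 4 days under other counting conventions. The size of the undercut rests on assumptions from outside the documents: with a 1 g/dL rise and linear loss over 60 to 120 days, the effective floor in the worst case is about 4.5 to 4.6 g/dL instead of 5.5 g/dL, and it moves back towards 5.5 as Screening is drawn later. How many candidates would be affected cannot be told from the documents, although Section 4.2 names red-cell transfusion among the treatments commonly used in this disease.

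This is a cheap improvement, not a threat to the trial's conclusions. The SAP reports early termination with 2 participants enrolled and data presented as listings only, so the present relevance is limited to those two participants and to any later protocol that reuses the text.

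**What to change.** Reconcile criterion 5 of Section 5.2 with criterion 5 of Section 5.1. Keep the first-dose condition and add one sentence: when the Screening hemoglobin was drawn inside the protocol's own 60-day post-transfusion window, the hemoglobin limits are applied to a repeat value taken outside that window and before randomization. Section 5.4 already provides for repeat Screening samples; this makes the repeat mandatory in one defined case.

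**What it achieves.** On the assumptions above, the part of the rise remaining at the qualifying sample falls from 0.92-0.96 g/dL to at most 1 - 61 / 120 = 0.49 g/dL at 61 days. It does not remove donor cells altogether. It holds the eligibility sample to the interval the protocol already accepts at first dose.

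**Cost.** One sentence and a repeat blood count for the few recently transfused candidates. In the extreme case the repeat falls on about Day -1 or Day 1. Central laboratory testing is the default (Section 10.2), so first dose may slip by some days, and a Screening sample drawn on Day -56 would then fall outside the 56-day window, so other Screening tests might need repeating. Drawing the Screening sample later avoids this.

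**For the study as it ended.** Compare any transfusion dates of the two enrolled participants with their Screening hemoglobin dates. The planned listings of prior therapies and procedures and of laboratory values should allow this without new outputs.
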